#### 3.4.1.1 Best Overall Response

Best overall response (BOR) will be based on all post-baseline disease assessments that occur prior to the initiation of subsequent anticancer treatment. If re-treatment is permitted following an initial disease progression, a BOR will be reported separately for the re-treatment period. BOR will be summarized with the number and percentage of subjects for

the following categories: complete response (CR); partial response (PR); stable disease (SD); progressive disease (PD); and non-evaluable (NE).

At least 6 weeks from randomization (dose expansion) / the first dose of IP (dose escalation) first dose of IP must elapse without a radiological disease progression in order to assign a best overall response of SD. The definition of 6 weeks will allow for the protocol-defined disease assessment window of 3 days. Confirmation of PR and CR is required and must occur no fewer than 4 weeks after initial documentation of PR or CR. If a PR or CR that is pending confirmation is designated at an assessment followed by 1 or more non-evaluable assessments for CR or 1 or more non-evaluable assessments or assessments of SD for PR, response may be confirmed thereafter. Confirmation of PD is required in the dose escalation phase, but not the dose expansion phase. A confirmed PD will be a documented occurrence of a PD that is confirmed by a consecutive repeat assessment no fewer than 4 weeks later. A PD that occurs without follow-up scans to provide confirmation or only non-evaluable follow-up scans will also be considered a "confirmed" PD.

Concordance/discordance of disease assessment by investigator and derived disease assessment will be summarized in frequency table.

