## 2.2 Study Design

This is a multicenter, open-label, Phase 1/2 study to evaluate the safety, tolerability, PK, immunogenicity, and antitumor activity of MEDI0680 in combination with durvalumab or nivolumab monotherapy in adult immunotherapy-naïve subjects with selected advanced malignancies.

The study includes 2 phases, dose-escalation and dose-expansion. In the dose-escalation phase, subjects with selected solid tumors will receive MEDI0680/durvalumab combination therapy. In the dose-expansion phase, subjects with ccRCC will receive either MEDI0680/durvalumab combination therapy or nivolumab monotherapy.

[figure not shown]
In the dose-escalation phase, subjects may receive treatment for up to 12 months; in the dose expansion phase, subjects may remain on treatment until unacceptable toxicity, confirmed progressive disease (PD), or development of other reason for treatment discontinuation. Subjects in dose expansion may receive investigational product(s) (IP) for a maximum of 2 years. All subjects will be evaluated regularly. Clinical status will be classified according to modified RECIST 1.1 for subjects in the dose-escalation phase and by RECIST 1.1 for subjects in the dose expansion phase, and other disease-specific assessments. All subjects will be followed for survival until the end of study. Adverse events (AEs) and serious AEs (SAEs) will be followed.

In the dose-escalation phase, subjects will be enrolled using a 3+3 dose escalation design in 1 of 6 dose-level treatment groups: 0.1 mg/kg MEDI0680 Q2W with 3 mg/kg durvalumab Q2W, and increasing dose levels of MEDI0680 Q2W (0.1, 0.5, 2.5, 10, and 20 mg/kg) with 10 mg/kg durvalumab Q2W. The dose-escalation phase will initially include immunotherapy-naïve subjects with solid tumors. As of Protocol Amendment 2, only subjects with non-small cell lung cancer (NSCLC), squamous cell carcinoma of the head and neck (SCCHN), microsatellite instability-high (MSI high) colorectal cancer (CRC), bladder

cancer, ovarian cancer, esophageal cancer, gastric cancer, or renal cell carcinoma (RCC) will be enrolled.

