## 2.2.1 Treatment Regimen

Subjects will be treated in either the dose-escalation or dose-expansion phase. MEDI0680, durvalumab and nivolumab will be administered via IV infusion. In dose-escalation phase, subjects will remain on treatment for up to 12 months. In the dose-expansion phase, subjects will remain on treatment until unacceptable toxicity, confirmed PD, or development of other reason for treatment discontinuation.

In the dose-escalation phase only, subjects who achieve and maintain DC (ie, CR, PR, or stable disease [SD]) through the end of the 12-month treatment period will enter follow-up. During the first 12 months of follow-up, if the subject has PD, the subject may be re-administered MEDI0680 and durvalumab for up to another 12 months with the same treatment guidelines followed during the initial 12-month period if the subject fulfills the criteria for re-treatment in the setting of PD, has not received other anticancer treatments for their disease, and does not meet any of the IP discontinuation criteria as described in the protocol. Only 1 round of re-treatment will be allowed.

Nivolumab will be administered according to the package insert guidelines.

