## 3.4 Efficacy Analyses

## 3.4.1 Efficacy Endpoints and Analyses

The efficacy endpoints include best overall response (BOR); objective response (OR); disease control (DC); time to response (TTR); duration of response (DR); progression-free survival (PFS); overall survival (OS); and change from baseline in target lesion sum of diameters. All efficacy analyses will be analyzed based on the As-treated Population. Additional summaries may be presented for the Re-treated and/or Response-evaluable Populations. Time to disease assessments (TDA) will also be summarized.

For the dose escalation phase, efficacy analyses will be based on both an application of Response Evaluation Criteria in Solid Tumors (RECIST) 1.1 to investigator assessed tumor measurements and an application of *modified* RECIST 1.1 to investigator assessed tumor measurements. For the latter, RECIST 1.1 has been modified to require confirmation of PD. A confirmed PD will be a PD confirmed by a consecutive repeat assessment no fewer than 4 weeks later. A PD that occurs without follow-up scans to provide confirmation or only non-evaluable follow-up scans will also be considered a confirmed PD. No such modification will be made in the dose expansion phase.

In the expansion phase, efficacy analyses will be based on an application of RECIST 1.1 to investigator assessed tumor measurements and may also be based on the Blinded Independent Central Review (BICR) if such data is collected.

Time-to-event data will be summarized using Kaplan-Meier estimates (median time and two-sided 95% CI for median time). An 80% CI for median time *may* also be included.

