#### 3.4.1.5 Duration of Response

Duration of response (DR) is defined as the time from the first documentation of a subsequently confirmed objective response until the first documentation of disease progression or death due to any cause, whichever occurs first. Only subjects who have achieved objective response will be evaluated for DR. DR is defined in months as follows:

DR (months) = (Date of PD/death or censoring – Date of first subsequently confirmed disease response + 1) / (365.25/12),

such that date of PD/death or censoring is given in Table 3.2. The median DR and its 95% CI will be estimated using the Kaplan-Meier method. An 80% CI for median time *may* also be included.

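### The expansion-phase BOR rule does not stop at the first RECIST 1.1 progression, so a response after PD can count in the primary ORR while the same subject is already a PFS event

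*SAP*

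**What the plan says.** - **BOR window (SAP 3.4.1.1).** "Best overall response (BOR) will be based on all post-baseline disease assessments that occur prior to the initiation of subsequent anticancer treatment". ORR (3.4.1.2) is taken directly from BOR.
- **Other mentions of progression in the BOR rule.** There are two. The first is "If re-treatment is permitted following an initial disease progression, a BOR will be reported separately for the re-treatment period"; section 2.2.1 offers re-treatment in dose escalation only. The second is a minimum period for stable disease, which "must elapse without a radiological disease progression in order to assign a best overall response of SD". Neither limits CR or PR in expansion.
- **Criteria in expansion.** Section 3.4.1 describes the modified RECIST 1.1 used in escalation, which requires confirmed PD, and adds: "No such modification will be made in the dose expansion phase". Section 3.4.1.1 repeats it: "Confirmation of PD is required in the dose escalation phase, but not the dose expansion phase".
- **Treatment in expansion (2.2.1).** "subjects will remain on treatment until unacceptable toxicity, confirmed PD, or development of other reason for treatment discontinuation". Section 2.2 has the same rule with "may" in place of "will".
- **PFS and DR.** PFS ends at the first documented PD, which Table 3.2 dates at its earliest sign. DR (3.4.1.5) runs from the first response that is later confirmed "until the first documentation of disease progression or death due to any cause, whichever occurs first", and its formula takes the end date from the same Table 3.2.
- **Go/NoGo (section 4).** Futility looks count confirmed and unconfirmed responses; the final analysis counts confirmed ones. Neither mentions a cut at PD.

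**The concern.** Under unmodified RECIST 1.1 without PD confirmation, the first PD is the progression event in expansion. The design nevertheless keeps subjects on treatment past it until PD is confirmed, so later scans will exist. The BOR rule takes in all of them up to the next anticancer therapy.

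Two things are at stake. First, the primary endpoint: responses seen only after progression would enter the RECIST 1.1 ORR, although the SAP has a separate exploratory irRECIST analysis (objective 6 in section 2.1.3; section 3.4.2) where they belong. Second, coherence: ORR, PFS and DR could tell different stories about the same subject, and the SAP has no rule to settle it.

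**Working it through.** **1. Does the derivation allow a response after PD?** Section 3.3.5.1 derives target-lesion response and overall response visit by visit, and no step carries an earlier PD forward. Take a constructed subject with target lesions only and no new lesions. Visits are 8 weeks apart, inferred from section 3.4.1.6, where 17 weeks is two assessments plus one week.

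| Visit | Sum (mm) | Change from nadir | Change from baseline | Derived response |
|---|---|---|---|---|
| Baseline | 100 | – | – | – |
| Week 8 (day 57) | 125 | +25%, +25 mm | +25% | PD |
| Week 16 (day 113) | 65 | −35% (nadir 100) | −35% | PR |
| Week 24 (day 169) | 60 | −8% (nadir 65) | −40% | PR, confirmed 8 weeks later |

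With no other anticancer therapy, all three visits fall inside the BOR window. BOR is confirmed PR and the subject is a primary-endpoint responder.

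**2. PFS for this subject.** The event is at week 8: (57 − 1 + 1)/30.4375 = 1.9 months, with randomization as day 1 and 365.25/12 = 30.4375.

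**3. DR for this subject.** There are two readings of the DR definition.
- Same PD as for PFS: (57 − 113 + 1)/30.4375 = −55/30.4375 = −1.8 months.
- First PD after the response: DR is positive, but its progression date differs from the one used for PFS.

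The SAP does not choose between them. The two endpoints are inconsistent either way.

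**4. Size per subject.** 1/40 = 2.5 points of ORR in the combination arm; 1/20 = 5 points in the nivolumab arm.

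**5. Effect on the final Go decision.** The inputs from section 4 are 40 versus 20 subjects, a target difference of 20 points, and Go if P(δ > 20%) exceeds 70%. The SAP gives no prior, so independent Beta(1,1) priors are assumed. P(Go) is the sum of binomial probabilities over those of the 41 × 21 outcomes that meet the Go criterion.

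Against the plan's own figures (Table 4.1, benchmark 25%), this model does not match:

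| True difference | Table 4.1 | Model |
|---|---|---|
| 20 points, Go | 28% | 24.5% |
| 20 points, NoGo | 7% | 11.6% |
| 30 points, Go | 67% | 55% |

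The results below therefore show direction and rough size only.

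| True ORR without post-PD responses | Gain from post-PD responses | P(Go), combination arm gains only | P(Go), both arms gain equally |
|---|---|---|---|
| 45% vs 25% | 0 | 0.245 | 0.245 |
| 45% vs 25% | 2.5 points | 0.314 | 0.249 |
| 45% vs 25% | 5 points | 0.390 | 0.253 |
| 40% vs 25% | 0 | 0.133 | 0.133 |
| 40% vs 25% | 2.5 points | 0.184 | 0.139 |
| 40% vs 25% | 5 points | 0.245 | 0.143 |

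The effect on the decision comes almost wholly from unequal gains between arms.

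**6. What is not in dispute.** The sample-size figures in section 2.4 hold on their own inputs. The pooled normal formula for 47.5% versus 21.5% at one-sided 0.10 gives 76.9% power (stated 76%), and the exact interval for 19/40 is 31.5% to 63.9%, as stated. The defect is in the endpoint rule.

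**The case against.** **The wording may be incomplete rather than a decision.** Expansion is declared to be unmodified RECIST 1.1, and the BOR section says PD needs no confirmation there. It also lets a pending response be confirmed across non-evaluable or, for PR, stable visits, and does not mention PD. All this suggests that a cut at PD was intended. A reader should not infer that the sponsor chose to count responses after progression. But the cut is nowhere written, and the window that is written is explicit and different. A programmer who follows it would count these responses.

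**Negative DR is not a certain result.** An interval running from response until progression can naturally mean the first PD after that response. This stands: a reader might infer that the SAP produces negative durations, but it does so only on one reading. The reference to Table 3.2 favours that reading without settling it. The other reading leaves DR and PFS with different progression dates.

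**Bias in favour of the combination is not shown.** A reader might infer that open-label continuation past PD would add responders mainly in that arm. The treatment rule is the same for both arms, and nothing in the SAP documents different continuation. The larger P(Go) shifts assume unequal gains.

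**The cases may be rare.** A PR after PD through target growth needs the sum to fall at least 30% below baseline and to be confirmed at least 4 weeks later. There must also be no non-target PD, no new lesion recorded as present, and no other therapy. This stands: the number is unknown and may be nil.

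**Conclusion.** The BOR rule is wrong as written for the expansion phase and should be corrected. Taken literally, a confirmed CR or PR after a first RECIST 1.1 PD counts in the primary ORR and in the final Go/NoGo, and the interim looks share the exposure without needing confirmation. The same subject has a PFS event at the earlier PD, and DR is either negative or inconsistent with PFS. No other section of the SAP repairs this.

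The contradiction follows from the text alone. Its numerical effect does not: it is 2.5 or 5 ORR points per subject, times a number that the SAP does not give. The P(Go) figures rest on an assumed prior that does not reproduce Table 4.1 and on assumed gains; they are small when both arms gain equally. The documents do not support a claim that the trial's conclusion would change or that one arm is favoured.

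**What to change.** In section 3.4.1.1, state that BOR by RECIST 1.1 uses assessments up to and including the first PD, or up to the start of subsequent anticancer treatment, whichever comes first. For modified RECIST 1.1 in dose escalation, the corresponding point is the first confirmed PD.

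In section 4, apply the same cut to the responses used in the interim and final Go/NoGo. Report responses that appear only after RECIST 1.1 progression under irRECIST (section 3.4.2) and nowhere else. With this cut, no counted expansion response can follow the PD that ends PFS, so the DR conflict disappears.

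The cost is one sentence in the BOR section, a matching line in section 4 and one programming condition. ORR may be slightly lower. The rule on how long subjects stay on treatment need not change; only the endpoint definition has to allow for it.

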#### 3.4.1.3 Disease Control

Disease control rate - 8 (DCR8) is defined as the proportion of subjects with a BOR of confirmed CR, confirmed PR, or SD (maintained for ≥ 8 weeks). A similar definition applies to DCR24. Duration of SD is defined as the time from randomization (dose expansion) / the first dose of IP (dose escalation) until the first documentation of disease progression or death due to any cause, whichever occurs first, and will allow for the protocol-defined disease assessment window of 3 days. DCR8 and DCR24 will be estimated with a 95% CI using the exact probability method. For the expansion phase, an estimate of the difference in DCR8 and DCR24 between treatment groups will be reported and tested for significance with a Pearson chi-square test (or Fisher's exact test, as appropriate).

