If a subject has two or more consecutive completely missed or non-evaluable assessments followed immediately by death or an assessment showing radiologic disease progression, then the subject will be censored for PFS. PFS will be censored at the date of randomization (dose expansion) / the first dose of IP (dose escalation) or the last progression-free disease assessment prior to the missed or non-evaluable assessments, whichever occurred last. If a subject has two or more consecutive missed or non-evaluable assessments followed by an assessment showing no radiologic disease progression, then the assumption will be that the subject did not progress during the missed or non-evaluable assessments. Two or more consecutive assessments is defined as  $\geq 17$  weeks (two disease assessments as per protocol plus a 1 week visit window to allow for a late assessment) after the last evaluable post-baseline disease assessment.

Subjects remaining on study without radiologic disease progression or death at the time of analysis will be censored for PFS at the date of their last adequate disease assessment. An adequate assessment is one that has recorded measurements for all target lesions and statuses for all non-target lesions defined at baseline (ie, the last non-missing or non-evaluable disease assessment). Additionally, a sensitivity analysis may be performed censoring PFS at the date of the last progression-free disease assessment prior to initiation of subsequent anticancer treatment.

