## 3.4.2 Additional Analyses of the Efficacy Endpoints

Disease Response will also be assessed based on an application of immune-related Response Evaluation Criteria in Solid Tumors (irRECIST) (Nishino et al, 2013) to investigator assessed tumor measurements. All new lesions meeting measureable criteria will be included in the Tumor Burden. Objective Response by irRECIST is defined as immune-related complete response (irCR) or immune-related partial response (irPR) with confirmation required occurring no fewer than 4 weeks after initial documentation of irCR or irPR. If an irPR or irCR that is pending confirmation is designated at an assessment followed by 1 or more non-evaluable assessments or assessments of irSD, response may be confirmed thereafter Disease Control - 8 by irRECIST is defined as confirmed irCR, confirmed irPR, or immune-related stable disease (irSD) (maintained for ≥ 8 weeks). A similar definition applies

to Disease Control - 24. Duration of irSD is defined as the time from randomization (dose expansion) / the first dose of IP (dose escalation) until the first documentation of disease progression or death due to any cause, whichever occurs first, and will allow for the protocoldefined disease assessment window of 3 days. Concordance/discordance between RECIST 1.1 and irRECIST disease assessment will be summarized in frequency table.

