Upon enrollment of 60 subjects in the dose-expansion phase, a final analysis will be performed. NoGo criteria will be met if the probability that the  $\delta$  exceeds the pre-specified

[figure not shown]
target of 20% is less than 10% (ie, NoGo:  $P[\delta > Target] < 10\%$ ). Go criteria will be met if the probability that the  $\delta$  exceeds the pre-specified target of 20% is more than 70% (ie, Go:  $P[\delta > Target] > 70\%$ ). For futility analyses, a response is defined as either a confirmed or unconfirmed CR or PR as per RECIST 1.1 and for the final analysis a response is defined as a confirmed CR or PR as per RECIST 1.1.

At interim analyses, efficacy and selected safety data will be summarized to assess the overall benefit-risk profile. The analysis populations to be used for the interim analysis are described below:

- As-treated with 17 weeks of potential follow up is defined as all subjects in the Astreated Population who have a baseline disease assessment and have an opportunity to be followed for at least 17 weeks (i.e., received the first dose of MEDI0680, durvalumab or nivolumab, whichever earliest, at least 17 weeks ago). The 17 weeks are to have at least 2 post-baseline disease assessments plus the one week visit window. This is the primary analysis population for the interim analysis of efficacy data.
- Response evaluable with 17 weeks of potential follow up is defined as all subjects in the As-treated Population who 1) have a baseline disease assessment; 2) have an opportunity to be followed for at least 17 weeks; and 3) have any post-baseline disease assessments or experience clinical PD/death. This is the secondary analysis population for the interim analysis of efficacy data.
- As-treated with 9 weeks of potential follow up is defined as all subjects in the Astreated Population who have a baseline disease assessment and have had an opportunity to be followed for at least 9 weeks. The 9 weeks are to have at least 1 post-baseline disease assessments plus one week visit window. This is the exploratory analysis population for the interim analysis of efficacy data.
- **As-treated Population**, as defined in section 3.2, is the primary analysis population for the interim analysis of safety data.

Figure 4-1 Decision Matrices for Continuous Monitoring

(MEDI0680 + Durvlumab vs Nivolumab: 10% false negative if effect = 20%)

[figure not shown]
[figure not shown]

Figure 4-2 Visual Joint Predictive Probability Operating Characteristics

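### The SAP uses two windows for the same scans, 3 days and 1 week; if 1 week is the true one, the 17-week PFS cut can censor progression found after a single missed scan

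*SAP*

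**What the plan says.** Three rules use a 3-day window:

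- Section 3.4.1.1, minimum time for a best overall response of SD: "The definition of 6 weeks will allow for the protocol-defined disease assessment window of 3 days".
- Section 3.4.1.3, duration of SD for DCR8 and DCR24: "will allow for the protocol-defined disease assessment window of 3 days".
- Section 3.4.2, duration of irSD for disease control by irRECIST: "will allow for the protocoldefined disease assessment window of 3 days".

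Two rules use 1 week:

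- Section 3.4.1.6, under the censoring of PFS, sets the equivalent of two consecutive missed assessments at 17 weeks or more, explained as "two disease assessments as per protocol plus a 1 week visit window to allow for a late assessment". The clock starts "after the last evaluable post-baseline disease assessment".
- Section 4 defines the main interim efficacy population in the same way: "The 17 weeks are to have at least 2 post-baseline disease assessments plus the one week visit window". Its 9-week population is built on one assessment plus the same week.

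The consequence of meeting the PFS definition is stated in section 3.4.1.6. Two or more missed or non-evaluable assessments are "followed immediately by death or an assessment showing radiologic disease progression, then the subject will be censored for PFS". Table 3.2 gives the same rule, and section 3.4.1.5 takes the censoring dates for duration of response from that table.

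**The concern.** Both figures are offered as the window around the same scheduled disease assessments, and only the 3 days is called protocol-defined. A difference between study phases does not explain the two values. The SD, disease-control, irRECIST and PFS rules each name dose expansion, and the interim rule concerns expansion only.

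Two things depend on the answer. The first is the day on which SD counts as maintained for 24 weeks. The second is whether the 17-week cut does what Table 3.2 intends, which is to censor only after at least two consecutive missed or non-evaluable assessments. DCR24 and PFS are both tested between arms. With up to 40 and 20 subjects, one reclassified subject moves a rate by 1/40 = 2.5 or 1/20 = 5 percentage points.

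**Working it through.** **Inputs.** Windows of 3 days (sections 3.4.1.1, 3.4.1.3, 3.4.2) and 1 week (sections 3.4.1.6 and 4); a cut of 17 weeks = 119 days from the last evaluable scan (section 3.4.1.6). The SAP does not state the scan interval, so it is inferred here.

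**Reproducing the SAP's figures.** (17 − 1)/2 = 8 weeks and 9 − 1 = 8 weeks, so both imply 8-weekly scans. In reverse, 2 × 8 + 1 = 17 and 1 × 8 + 1 = 9. The stated figures reproduce exactly.

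**Gap after missed scans.** With m missed scans, the gap from the last evaluable scan to the next one is (m + 1) × 56 days + (offset of next scan) − (offset of last scan). For m = 1 the nominal gap is 112 days; for m = 2 it is 168 days.

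| Window | One missed scan (days) | Share of one-missed gaps at or above 119 days* | Two missed scans (days) |
|---|---|---|---|
| ±7 days | 98–126 | 36/225 = 16% (12.5% in continuous time) | 154–182 |
| 0 to +7 days | 105–119 | 1/64 = 1.6% | 161–175 |
| ±3 days | 106–118 | 0 | 162–174 |

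*Assumes independent scan days spread uniformly over the window; the SAP gives no distribution.

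For ±7 days in whole days, the next scan must fall at least 7 days later within its window than the last one did. The number of such pairs is 8 + 7 + 6 + 5 + 4 + 3 + 2 + 1 = 36, out of 15 × 15 = 225. In continuous time the share is 7²/(2 × 14²) = 12.5%. For the late-only window, only an on-time last scan followed by a scan 7 days late qualifies: 1 of 8 × 8 = 64. It qualifies because the rule includes exactly 17 weeks.

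**Thresholds for SD.**

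| Rule | Nominal | Less 3 days | Less 7 days |
|---|---|---|---|
| 6-week SD minimum | 42 | 39 | 35 |
| DCR8 | 56 | 53 | 49 |
| DCR24 | 168 | 165 | 161 |

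The third scan is nominally on day 3 × 56 = 168. Under ±7 days it falls on days 161–175, and 4 of those 15 days (161–164) lie between the two thresholds. A subject with SD whose progression is found on one of those days fails DCR24 with a 3-day allowance and passes with 7. Under a late-only week (days 168–175) or ±3 days (days 165–171), no in-window third scan falls there.

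The first scan under ±7 days is no earlier than day 56 − 7 = 49, already past the 42-day SD minimum. Progression at that scan gives a best response of PD, so the subject is not counted in DCR8 under either allowance.

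**Deaths.** A death can fall on any day, so the two-missed ranges above do not apply to it. After an on-time last scan, assessments fall due on days 56 and 112, and the late week for the second ends on day 119. A death at 17.5 weeks (about day 122) with neither scan done follows two missed assessments, and the present cut censors it as Table 3.2 intends.

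**The case against.** The strongest defence is that 3 days is the only window the SAP calls protocol-defined. If it is two-sided and correct, the 17-week cut separates one missed scan (at most 118 days) from two (at least 162 days) without error. The week in section 3.4.1.6 could then be read as a harmless analysis margin. The part about the cut stands: under ±3 days it should not be touched. The margin reading is weaker, because sections 3.4.1.6 and 4 both call the week a visit window and neither says that a different tolerance was intended.

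The 16% is also the least favourable case. The SAP describes the week as allowing for a late assessment, which reads as late-only and gives 1.6%. The range across plausible windows is therefore 0 to 16%, on an assumed uniform spread. The denominator is small as well: subjects who missed exactly one scan and had progression at the next, out of at most 60. This stands and keeps the point minor.

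A reader might go further and infer that DCR8 and the 6-week SD minimum are materially distorted. On the implied schedule they are hardly affected. A reader might also infer that, if 3 days is right, the 17- and 9-week figures must be shortened. They need not be: the PFS cut performs correctly, and the interim populations only require an opportunity for follow-up, where a few spare days do no harm.

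**Conclusion.** The inconsistency is certain from the text: the same assessments have a 3-day window in three rules and a 1-week window in two, and all five apply to dose expansion. Which is right cannot be settled without the protocol.

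The effect on the PFS cut is conditional. If the window is 1 week, as the rule's own rationale says, the cut can censor progression found after one missed scan, contrary to Table 3.2: 12.5–16% of one-missed gaps under ±7 days, 1.6% if late-only. If it is ±3 days, no in-window scan is misclassified. It would therefore be wrong to conclude that the cut misclassifies subjects whatever the window.

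For DCR24 the threshold differs by 4 days (165 against 161). For in-window scans this matters only under a two-sided week.

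These results rest on the inferred 8-week interval, and the percentages on uniform scan days. PFS and, through Table 3.2, duration of response are exposed to the cut. The primary ORR endpoint is not affected. Few subjects would change status, so this is a minor correction.

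**What to change.** Reconcile the five places (sections 3.4.1.1, 3.4.1.3, 3.4.2, 3.4.1.6 and 4) with the protocol and state one window, including whether it is two-sided.

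- **If it is 1 week:** allow 7 days in the SD and disease-control rules. For progression found at a scan, either count missed scheduled assessments directly or set the cut above the largest one-missed gap: more than 18 weeks (126 days) for ±7 days, more than 17 weeks (119 days) for late-only. For deaths, count the scheduled assessments actually missed. A flat cut of more than 18 weeks would turn some deaths at 17–18 weeks, after two truly missed scans, into events against Table 3.2.
- **If it is 3 days:** keep the 17-week PFS cut and correct only the stated 1-week rationale in sections 3.4.1.6 and 4.

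The cost is SAP wording and, in the 1-week case, a small change to the PFS and duration-of-response derivations. No new data are needed beyond scheduled and actual assessment dates.

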#### 3.4.1.6 Progression-free Survival

Progression-free survival (PFS) is defined as the time from randomization (dose expansion) / the first dose of IP (dose escalation) until the first documentation of disease progression or death due to any cause, whichever occurs first, regardless of whether the subject receives subsequent anticancer therapy prior to progression. Subjects who have not progressed at the time of analysis will be censored at the time of the latest date of assessment from their last adequate progression free disease assessment. Censoring rules are presented in Table 3.2. PFS is defined in months as follows:

PFS (months) = (Date of PD/death or censoring – Date of randomization (dose expansion) / the first dose of IP (dose escalation) first dose of IP+1) / (365.25/12)

The median PFS and its 95% CI will be estimated using the Kaplan-Meier method. An 80% CI for median time *may* also be included.

For the expansion phase, the difference in PFS between treatment groups will be tested for significance with a logrank test. The hazard ratio for the two treatment groups with two-sided 95% CI will be estimated by a Cox proportional hazard model controlling for the prespecified stratification factors as explanatory variables in the model. The proportion of subjects progression free and alive at 6 months and associated 95% CI will be estimated using the Kaplan-Meier method.

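### In the dose-escalation modified RECIST 1.1 analysis, the literal PD confirmation rule leaves the first PD of a PD–NE–PD sequence unconfirmed, although PD–NE alone counts as confirmed

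*SAP*

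**What the plan says.** Section 3.4.1 provides two escalation analyses of investigator measurements, one by RECIST 1.1 and one by a modified version. For the second, "RECIST 1.1 has been modified to require confirmation of PD". Section 3.4.1.1 sets the scope: "Confirmation of PD is required in the dose escalation phase, but not the dose expansion phase".

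A PD can be confirmed in two ways.
- By a repeat scan: "A confirmed PD will be a documented occurrence of a PD that is confirmed by a consecutive repeat assessment no fewer than 4 weeks later" (Section 3.4.1.1; Section 3.4.1 says the same).
- By exception: "A PD that occurs without follow-up scans to provide confirmation or only non-evaluable follow-up scans will also be considered a confirmed PD".

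For responses, Section 3.4.1.1 deals expressly with intervening scans. If a pending CR or PR is "followed by 1 or more non-evaluable assessments for CR or 1 or more non-evaluable assessments or assessments of SD for PR", then "response may be confirmed thereafter". Section 3.4.2 gives a similar allowance for irCR and irPR. Neither section gives one for PD.

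On dating, PFS runs "until the first documentation of disease progression or death due to any cause, whichever occurs first" (Section 3.4.1.6). Table 3.2 dates the event at the earliest indication of progression. Section 3.3.5.4 takes the first date on which a diagnostic test indicates PD. None of the three says how confirmation at a later assessment sets the date.

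**The concern.** An NE scan does not break confirmation of a response but, as worded, it breaks confirmation of a progression. A subject with PD followed only by NE progresses at the first PD. A subject with the same two scans and then a second PD has stronger evidence of progression, yet can be given a later date.

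The pattern is foreseeable. Under Section 3.3.5.1, one missing target or non-target lesion makes an assessment NE unless PD is otherwise shown.

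What is at stake is the consistency of PFS, and in some sequences of DCR24 and DR, in the analysis that carries the secondary escalation objective on antitumor activity (Section 2.1.2). As the text stands, two programmers could also derive different dates from the same scans.

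**Working it through.** The plan gives no figure to reproduce here. The check applies the written rule to short scan sequences.

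**Inputs**
- Confirmation rule and exception: Sections 3.4.1 and 3.4.1.1.
- PFS formula (Section 3.4.1.6): months = (days from first dose to event + 1) / (365.25/12), where 365.25/12 = 30.4375.
- Scan interval: not stated outright. Section 3.4.1.6 equates two assessments plus a 1-week window with 17 weeks, so (17 − 1)/2 = 8 weeks. This is an inference.

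**Dates**
- Week 8: (56 + 1)/30.4375 = 1.87 months.
- Week 24: (168 + 1)/30.4375 = 5.55 months.
- Difference: 16 weeks, 112/30.4375 = 3.7 months.

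**Sequences, first PD at week 8, 8-weekly scans.** The last column ignores intervening NE scans, as the SAP does for CR and PR.

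| Scans from week 8 | How PD is confirmed as written | Event as written | Event if NE is bridged |
|---|---|---|---|
| PD | first PD, no follow-up | week 8 | week 8 |
| PD, NE | first PD, only NE follow-up | week 8 | week 8 |
| PD, PD | first PD, consecutive repeat | week 8 | week 8 |
| PD, NE, PD | second PD, no follow-up | week 24 | week 8 |
| PD, NE, PD, PD | second PD, consecutive repeat | week 24 | week 8 |

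**Sensitivity to the schedule.** Repeat scans are allowed from 4 weeks. With PD at week 8, NE at week 12 and PD at week 16, the event as written falls at (112 + 1)/30.4375 = 3.71 months, a delay of 8 weeks.

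**DCR24.** This needs an SD scan before the PD.
- SD week 8, PD week 16, NE week 24: SD lasts 16 weeks, so DCR24 is not met.
- The same plus PD at week 32: as written, SD lasts 32 weeks, so DCR24 is met.
- The same four scans with NE bridged: 16 weeks, not met.

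**Two NE scans.** In PD–NE–NE–PD at weeks 8, 16, 24 and 32, the gap from the first to the last PD is 24 weeks, which exceeds 17. If the first PD is unconfirmed, the missed-assessment rule (Table 3.2 and the text after it) could censor the subject at first dose, because no progression-free scan precedes the gap. PD–NE–NE without the last scan is an event at week 8. In PD–NE–PD the gap is 16 weeks, so that rule is not triggered.

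**The case against.** The strongest reply is that week 24 is not the only available reading. The PFS definition, Table 3.2 and Section 3.3.5.4 all point to the earliest evidence of progression, and Section 3.3.5.4 expressly covers modified RECIST 1.1. The exception for only-NE follow-up treats an NE scan like no scan, so consecutive could be meant as next evaluable. Both points have force, and week 24 should be called the literal reading, not the settled one. They do not close the gap. The three rules in Section 3.3.5.4 concern dates within one assessment and do not link separate assessments. The explicit bridge for CR and PR, with none for PD, weighs against reading one in.

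The second reply is that the reach is small, and this stands. The analysis is descriptive, and the sequence may be rare. The unmodified RECIST 1.1 analysis of the same subjects puts the event at the first PD, so any distortion would be visible.

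A reader might infer that PD–NE–PD by itself can meet DCR24. The SAP does not support that: no scan in the sequence shows SD, CR or PR, and the best overall response is PD. Nor does DR come into that sequence, since only responders enter DR.

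**Conclusion.** The point holds as a minor one. On the literal wording, the first PD of PD–NE–PD is unconfirmed while that of PD–NE is confirmed, and no other text clearly restores the first date. The PFS delay for such a subject is 16 weeks if scans are 8-weekly and about 8 weeks if they are 4-weekly after the first PD. The interval is inferred.

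DCR24 changes only when an SD scan precedes the pattern, and DR only in responders who later show it. Section 2.4 allows up to about 36 evaluable subjects in six groups. If that meant about six per group, one subject would move a group's DCR24 by 1/6, or about 17 percentage points.

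A reader might infer a general upward bias in PFS, or an effect on the randomised comparison. Neither follows. Only subjects with this pattern are affected, and the SAP gives no basis for its frequency. The expansion phase, including its ORR comparison, does not require confirmation of PD.

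**What to change.** In Sections 3.4.1 and 3.4.1.1, state for modified RECIST 1.1 that:
- a PD is confirmed if the first evaluable assessment made at least 4 weeks after it shows PD;
- intervening non-evaluable assessments do not break confirmation;
- the event date for PFS, DR and duration of SD is the date of the first PD so confirmed.

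State also how an evaluable scan made before 4 weeks is treated. Keep the existing exception for no follow-up or only non-evaluable follow-up.

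With this wording every sequence in the table above has its event at week 8. The cost is one or two sentences and a small program change, with no new data.
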